5.1.1 Primary Effectiveness Endpoint

- Change from baseline to Week 24 after last injection on the Wrinkle Severity Rating Scale (WSRS) [REDACTED].

The primary endpoint will be calculated as follows based on WSRS assessments [REDACTED] at Week 24 for the respective NLF: WSRS score at Week 24 after last injection – WSRS score at baseline.

[REDACTED]

[REDACTED]

5.1.2 Secondary Effectiveness Endpoints

[figure not shown]
- Proportion of subjects with any improvement, defined as a rating of + 1, + 2, or + 3, on the Investigator Global Aesthetic Improvement Scale (iGAIS) for each NLF at Week 24 after last injection, as assessed by the treating investigator.

This dichotomous endpoint will be determined based on iGAIS ratings at Week 24 for the respective NLF. It will be set to “Y” for ratings $\geq + 1$ and to “N” for ratings $< + 1$.

- Proportion of subjects with any improvement, defined as a rating of + 1, + 2, or + 3, on the Subject Global Aesthetic Improvement Scale (sGAIS) for each NLF at Week 24 after last injection, as assessed by the masked subject.

This dichotomous endpoint will be derived from sGAIS ratings at Week 24 for the respective NLF. It will be set to “Y” for ratings $\geq + 1$ and to “N” for ratings $< + 1$.

Calculation of proportions (relative frequencies) is described in [Section 6](#).

5.2 Safety Endpoints

For details on safety assessments see CSP [Section 11.2.2](#). For safety definitions and requirements, including definition of an adverse event (AE), severity grading for an AE, causal relationship of an AE with an Investigational medical device (IMD), outcome categories for an AE, definition of a serious adverse event (SAE), see CSP [Section 12](#).

Treatment-emergent AEs (TEAEs) are defined as AEs with onset at or after the first administration of trial treatment. If an AE starts prior to treatment but worsens at or after treatment, the investigator records this observation as a new AE with onset = time of worsening.

AEs not constituting TEAEs will be referred to as non-TEAEs.

For details on separation of TEAEs and non-TEAEs see Appendix, [Section 9.3](#).

End date or end time or AEs will not be imputed.

[figure not shown]
A device deficiency is defined as an inadequacy of a medical device with respect to its identity, quality, durability, reliability, safety, or effectiveness. Note: Device deficiencies include malfunctions, use errors, and inadequate labeling. For more information on device deficiencies, see CSP [Section 12.7](#).

[figure not shown]
5.2.1 Primary Safety Endpoint

Not applicable.

5.2.2 Secondary Safety Endpoint

- Incidence of TEAEs related to Radiesse, as reported by the treating investigator throughout the trial.

6 Statistical Analysis Methods

Metric statistics for continuous endpoints will be number of values analyzed (n), number of observed values (Nobs), mean, standard deviation (SD), median, lower quartile (Q1), upper quartile (Q3), minimum (min), and maximum (max), if not stated otherwise. Mean, quartiles and median will be reported to one decimal place more than the data were collected, for the standard deviation two decimal places more will be displayed; for derived data, the number of decimal places will explicitly be given in the sections below.

¹ Injection depth is included in list of additional data collected ([Section 11.2.3](#) of CSP version 2.0) but is not analyzed because these data are not collected in the case report form.

Frequency tables for qualitative endpoints will be absolute and percent frequencies (n, %). Cross tables will include number of subjects with non-missing data at the corresponding visit. Percentages will be calculated using the denominator of all subjects in a specified population or random group (only needed for selected disposition tables in [14.1](#)). For TEAE analyses on the SES, which will be conducted by actual treatment (see [Section 4](#)), the denominator for calculation of percentages per treatment will be adapted to the number of subjects in SES treated with the respective treatment. For analyses on observed cases (OC), percentages will be calculated using the number of subjects with non-missing data (Nobs) at the corresponding visit as denominator. The denominator will be specified in a footnote to the tables for clarification if not otherwise obvious.

The total number of subjects in a given analysis set (as defined in [Section 4](#)) will be referred to with N.

Percentages will be reported to one decimal place. If not otherwise specified, statistical tests will be conducted two-sided at type I error rate 5%. P values will be reported to four decimal places (e.g., p=0.0375). P values below 0.0001 will be presented as '<0.0001'. P values above 0.9999 will be presented as '>0.9999'. Confidence intervals (CIs) will be two-sided 95% CIs.

Detailed information on effectiveness, safety, and other data will be provided in listings.

All statistical analyses will be performed using Statistical Analysis System (SAS) statistical analysis software (Version 9.4).

6.1 Effectiveness Endpoints

Effectiveness endpoints are defined in [Section 5.1](#) [REDACTED]. Effectiveness data assessed at Week 4 post first injection will be listed only. There will be one confirmatory analysis of the primary effectiveness endpoint. [REDACTED]

6.1.1 Primary Effectiveness Endpoint

6.1.1.1 Primary analysis

If the expected mean intra-individual difference between Radiesse and Restylane in WSRS change from baseline to Week 24 is denoted by δ , the null and alternative hypotheses to be tested are:

$$H_0: \delta \geq 0.5 \text{ (null hypothesis) versus } H_1: \delta < 0.5 \text{ (alternative hypothesis)}$$

with 0.5 being the non-inferiority margin. To test the null hypothesis, a two-sided 95% CI will be constructed around the estimate for δ . H_0 will be rejected if the upper bound of the two-sided 95% CI lies below the non-inferiority margin of 0.5. It will then be concluded that Radiesse is non-inferior to Restylane and is effective. The two-sided 95% CI for δ will be constructed by applying a repeated-measures analysis of covariance (ANCOVA) model to the WSRS change from baseline to Week 24 after last injection. This model will include treatment (i.e., Radiesse or Restylane), investigative site, touch-up performed (i.e., yes/no), and random group (i.e., "Group 1: left NLF: Radiesse, right NLF: Restylane" or "Group 2: left NLF: Restylane, right NLF: Radiesse")² as fixed class effects and baseline WSRS [REDACTED] as a fixed covariate. That observations are dependent over treatment (due to the split-face design) will be modelled using treatment as a repeated factor. The SAS procedure "proc mixed" will be used with the covariance

² The term "randomized sequence" as used in [Section 13.4.1.1](#) of the protocol was replaced by "random group", as this is the more appropriate term for split-face design studies. Also, the two categories (group 1 and group 2) were relabeled by using the labels from protocol [Sections 10.3](#) and [13.2](#). These changes in terms/ category labels do not constitute any change in planned analyses since the new terms/labels refer to the same variable/ categories.

matrix for treatments left “unstructured”. The latter allows estimation of different variances for the two treatments.

The least squares means (lsmeans) statement will be used to derive a point estimate for δ as well as the associated two-sided 95% CI.

[REDACTED]

[REDACTED]

- In addition, the mean treatment difference in WSRS change from baseline to Week 24 after last injection with the associated 2-sided 95% Wald confidence interval will be presented [REDACTED]. The calculation will be performed as follows. First, the treatment difference on the primary endpoint will be calculated for each subject as WSRS change from baseline to Week 24 after last injection at NLF randomized to Radiesse – WSRS change from baseline to Week 24 after last injection at NLF randomized to Restylane. Second, the mean and further metric statistics statistics for continuous endpoints as specified in first paragraph of [Section 6](#) will be calculated for the treatment difference in WSRS change from baseline to Week 24 after last injection. [REDACTED]

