## 8 CLINICAL INVESTIGATION PLAN

### 8.1 Overview of Trial Design

This is a 48-week, prospective, randomized, multicenter, split-face, active-comparator, blinded [REDACTED] trial designed to evaluate the effectiveness and safety of Radiesse compared to Restylane for the correction of moderate to severe NLFs in healthy adult subjects. Those enrolled will have symmetrical NLFs, with the same WSRS score of 3 or 4 (moderate or severe) for both right and left NLFs, as determined on live assessment [REDACTED].

[REDACTED]

All [REDACTED] will be blinded to treatment assignment. [REDACTED] primary effectiveness will be evaluated using the change from baseline to Week 24 after last injection on the WSRS [REDACTED].

Subjects who do not achieve at least 1-point improvement on the WSRS at Week 4 when compared to baseline, [REDACTED] will have a touch-up injection in [REDACTED] NLFs to achieve optimal correction (i.e.,  $\geq 1$ -point improvement). If a touch-up is performed, the same randomized product assigned for the initial injection must be used. [REDACTED]

[REDACTED]

[REDACTED]

[REDACTED]

Standard safety parameters, including documentation of AEs and SAEs, will be assessed. [REDACTED]

After a maximum 10-day screening period, the planned trial duration for individual subjects is 48 weeks ( $\pm 7$  days) after last injection.

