#### 13.4.1.1 Primary Effectiveness Endpoint

If the expected mean intra-individual difference between Radiesse and Restylane in WSRS change from baseline to Week 24 is denoted by  $\delta$ , the null and alternative hypotheses to be tested are:

$$H_0 : \delta \geq 0.5 \text{ (null hypothesis ) versus } H_1 : \delta < 0.5 \text{ (alternative hypothesis)}$$

with 0.5 being the non-inferiority margin. To test the null hypothesis, a two-sided 95% CI will be constructed around  $\delta$ .  $H_0$  will be rejected if the upper bound of the two-sided 95% CI lies below the non-inferiority margin of 0.5. It will then be concluded that Radiesse is non-inferior to Restylane and is effective. The two-sided 95% CI for  $\delta$  will be constructed by applying a repeated-measures analysis of covariance (ANCOVA) model to the WSRS change from baseline to Week 24. This model will include treatment (i.e., Radiesse or Restylane), investigative site, touch-up performed (i.e., yes/no), and randomized sequence (i.e., “left NLF treated with Radiesse and right NLF treated with Restylane” or “left NLF treated with Restylane and right NLF treated with Radiesse”) as fixed class effects and baseline WSRS [REDACTED] as a fixed covariate. That observations are dependent over treatment (due to the split-face design) will be modelled using treatment as a repeated factor. The SAS procedure “proc mixed” will be used with the covariance matrix for treatments left “unspecified”. The latter allows estimation of different variances for the two treatments.

The least squares means (lsmeans) statement will be used to derive a point estimate as well as a 95% CI for  $\delta$ .

The confirmatory analysis will be based on the PPS. [REDACTED]  
[REDACTED] he  
variables (VAR) statement will include the variables treatment, investigative site,

randomized sequence, age, sex, touch-up, and WSRS at visits before Week 24. [REDACTED]

[REDACTED]

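### The confirmatory model adjusts for touch-up, which is decided after randomisation from Week 4 response: coded per fold it can move the estimate off the stated δ, coded per subject it does nothing

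*SAP*

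**What the plan says.** Protocol 13.4.1.1 and SAP 6.1.1.1 describe one confirmatory analysis: PROC MIXED on WSRS change to Week 24, treatment as the repeated factor, a free 2×2 covariance matrix, and non-inferiority if the upper 95% limit is below 0.5. The fixed effects are listed in the SAP as "This model will include treatment (i.e., Radiesse or Restylane), investigative site, touch-up performed (i.e., yes/no), and random group", and the protocol has the same term ("touch-up performed (i.e., yes/no), and randomized sequence"). Baseline WSRS is the covariate.

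The target δ is the "expected mean intra-individual difference between Radiesse and Restylane in WSRS change from baseline to Week 24". Change is "WSRS score at Week 24 after last injection – WSRS score at baseline", so a larger δ means that Radiesse is worse.

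Touch-up is for "Subjects who do not achieve at least 1-point improvement on the WSRS at Week 4 when compared to baseline" (Protocol 8.1). Protocol 10.5.2 allows it on one or both sides and withholds it when the investigator sees a contraindication or a worrying adverse event. Protocol 9.2.6.1 foresees that a subject may refuse it.

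The SAP also reports "the mean treatment difference in WSRS change from baseline to Week 24 after last injection with the associated 2-sided 95% Wald confidence interval" (bullet before 6.1.1.3), but as an extra presentation. SAP 6.1 adds: "Effectiveness data assessed at Week 4 post first injection will be listed only".

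**The concern.** Touch-up is an outcome of the randomised product at Week 4, not a baseline characteristic. If one product needs more touch-ups, holding touch-up fixed removes part of the product difference that δ is meant to capture. The coefficient β also mixes two things: any benefit of the second injection, and the fact that folds selected for it had responded poorly. It can therefore take either sign.

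The test is the only confirmatory one, and its confidence limit alone decides non-inferiority. If β and the rate difference (Radiesse minus Restylane) have the same sign, the shift favours Radiesse. If the signs are opposite, it works against Radiesse. If either is near zero, nothing material happens.

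**Working it through.** **Plan's own figure.** 100 / (1 − 0.15) = 117.6, rounded up to 118; 118 × 0.85 = 100.3. The 118 randomised and 100 in the PPS reproduce. No SD, touch-up rate or touch-up effect is visible, so those inputs below are assumptions.

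**Algebra.** Let d be a subject's Radiesse-minus-Restylane difference in change, and t the touch-up flag. Site, random group and baseline are equal on the two sides of a subject (equal baseline WSRS is an inclusion criterion, Protocol 9.2.1), so they cancel from d.

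- *Flag per subject:* it cancels too. With a free covariance matrix and complete pairs, δ-hat = mean(d) and SE = SD(d)/√n, with or without the term.
- *Flag per fold:* d has mean δ + β(t_Rad − t_Rest), so δ-hat = mean(d) − β-hat × (p_Rad − p_Rest), where p is the touch-up rate.

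**Numerical check by REML, n = 100.** In one data set mean(d) = 0.176982. With no term and with a per-subject term the estimate was 0.176982 and the SE 0.0803. With a per-fold term the estimate was 0.029415 with β-hat = 0.434. The gap, 0.1476, is 0.434 × 0.34, the observed rate difference being 0.34. Over 114,000 fits the identity held to 1e-14. The per-subject result needs complete pairs and equal baselines: in single test data sets the per-subject term moved δ-hat by 0.003 when baselines differed by side, and by 0.001 when 8 of 100 pairs were incomplete.

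**Size of shift.** For β from −0.5 to +0.5 and rate differences from −30 to +30 points, −β × (p_Rad − p_Rest) runs from −0.15 to +0.15, up to 30% of the margin.

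**Effect on error, by formula.** At true δ = 0.5, false non-inferiority is Φ(−1.96 + shift/SE), SE = SD/10, with SD of d from 1.0 to 0.7:

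- 0.02 towards Radiesse: 3.9–4.7%
- 0.05 towards Radiesse: 7.2–10.6%
- 0.10 towards Radiesse: 17–30%
- 0.05 against Radiesse: 0.4–0.7%

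**Effect on error, by simulation.** Integer WSRS, 100 pairs, 7 sites, per-fold flag triggered when that fold's Week 4 improvement is below 1 point (an assumed per-side rule), SD of d 0.83–0.88, true δ including touch-up = 0.5, 3,000 trials per cell (Monte Carlo SE about 0.3 points at 2.5%). False non-inferiority in %, nominal 2.5%:

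| Touch-up rate, Radiesse v Restylane | adds 0 | adds 0.3 | adds 0.6 | adds 1.0 |
|---|---|---|---|---|
| 10% v 10% | 2.4 | 2.9 | 1.9 | 2.3 |
| 15% v 10% | 7.6 | 5.5 | 3.6 | 2.1 |
| 20% v 10% | 17.7 | 9.3 | 5.1 | 1.9 |
| 30% v 10% | 51 | 25 | 9.0 | 1.2 |
| 10% v 20% | 0.0 | 0.3 | 0.6 | 3.2 |

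The 0-point column is extreme, since touch-up aims at a gain of 1 point or more. At 20% v 10% the mean β was 0.92 / 0.63 / 0.32 / −0.07. Multiplied by 0.10 and taken from 0.5, this gives 0.41 / 0.44 / 0.47 / 0.51, the mean estimates seen. There the model declared non-inferiority when the paired interval did not in 15.1 / 7.6 / 3.0 / 0.2% of trials. The unadjusted paired interval held 1.8–2.8% in all 20 cells.

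A second data model (35% v 15%, β = +0.5, expected shift 0.5 × 0.20 = 0.10, 1,000 trials) gave a mean estimate of 0.401 per fold against 0.502 per subject, and false non-inferiority of 19.8% against 2.3%.

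**Price of deletion if the flag is per fold.** Equal rates of 10 / 20 / 30%, power at true δ = 0.25:

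- Touch-up adds 0: SE 3.2 / 5.1 / 6.4% wider; power 81.2 to 79.1, 81.6 to 77.7, 85.1 to 79.8%.
- Adds 0.6: SE 1.2–1.8% narrower; power up 0.7–1.3 points.
- Adds 1.0: SE from 0.1% narrower to 1.7% wider; power from +0.1 to −1.7 points.

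At true δ = 0, power is at least 99.9% either way.

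**The case against.** The best counter-argument is that the harm exists only under a coding that the documents do not state. The term stands between site and random group, both subject-level; Protocol 8.1 words the trigger for subjects; and Protocol 11.1 times a single Week 24 visit from last injection. Under per-subject coding nothing is wrong with the estimate. Redactions follow the least-squares-means sentence, the laterality of touch-up in Protocol 8.1 is blacked out, and SAP 6.1.1.2 is not visible, so the coding level or a model without touch-up may be specified there. All of this stands, and it is why the conclusion is conditional.

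It also stands that the large figures need unequal rates, a weak touch-up and a true δ near the margin. When touch-up adds 1 point, error is 1.2–3.2% throughout.

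Touch-up by side should be recoverable from the by-visit injection listing (SAP, text after 6.2.2), and the paired interval would expose a shift. But neither governs the decision.

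Finally, a protocol edit needs ethics committee acknowledgement or approval (Protocol 14.4.2). The opening of Protocol 13, however, lets changed analyses be documented in the SAP, which answers most of that objection.

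**Conclusion.** The point holds as a conditional one. A factor decided after randomisation is in the only confirmatory model. Per subject, with complete pairs and equal baselines, it contributes nothing to δ-hat. Per fold, it shifts δ-hat by exactly −β-hat × (p_Rad − p_Rest). Even when the true rates are equal or β is zero, a single trial can show a small chance shift, but none is expected on average.

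Whether the shift matters here cannot be known from the documents. Under the assumed inputs, false non-inferiority at the margin ranges from nominal to several times nominal when Radiesse needs more touch-ups, and well below nominal in most cases when Restylane does. This is an inexpensive improvement to the plan, not proof that the analysis is invalid. Confidence is medium because the coding level is not visible.

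**What to change.** Delete the touch-up term from the fixed effects in SAP 6.1.1.1 and Protocol 13.4.1.1. With complete pairs and equal baselines, δ-hat then equals the paired difference that the SAP already computes. Keep touch-up in the protocol's VAR list ("randomized sequence, age, sex, touch-up, and WSRS at visits before Week 24"), which is a separate use. Tabulate touch-up rates by product, and label any touch-up-adjusted model exploratory.

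If the term is to stay, define it as one value per subject (any touch-up, yes or no). With complete pairs this gives the same δ-hat as deletion.

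Cost: one phrase in each document and one model term, settled before unblinding, with no new data. If the protocol text is amended as well, the ethics committee step applies. If the flag is already per subject and pairs are complete, the primary result does not change. If it is per fold with equal rates, the runs above put the change in SE between 1.8% narrower and 6.4% wider, and the change in power at δ = 0.25 between +1.3 and −5.3 points, with no loss at δ = 0.

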### 10.3 Methods of Assigning Subjects to Treatment Groups

Subjects who complete all screening assessments and meet all eligibility criteria will be randomized 1:1 to one of the following groups prior to injection:

- Group 1: left NLF: Radiesse, right NLF: Restylane
- Group 2: left NLF: Restylane, right NLF: Radiesse

Care must be taken to follow the subject's randomization assignment, ensuring that the Radiesse and Restylane syringes are injected in the randomly assigned NLF (left NLF or right NLF). Accurate documentation of which product (Radiesse or Restylane) is injected into which NLF (subject's right or left) is of critical importance in this trial.

This information will remain in the subject's source documents and be made available for verification of the proper randomization sequence by the sponsor or designee during monitoring visits.

Additional methodological details regarding randomization are provided in [Section 13.2](#).

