### **10.5.2 Selection and Timing of Treatment for Each Subject**

Subjects will have an initial injection at baseline (V2) on Day 1, as well as the option for a touch-up injection in one or both NLFs at Week 4 (V3). If a touch-up is performed, the same randomized product assigned for the initial injection must be used for touch-up injection. A touch-up treatment will only be administered if there are no medical contraindications or existing AEs of concern, as determined by the treating investigator.

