### 13.2 Randomization

Each subject screened will be given a screening number. Only the subjects who are randomized will receive a randomization number at baseline (V2) through an electronic system. All eligible subjects will be randomized 1:1 to one of the following groups:

- Group 1: left NLF: Radiesse, right NLF: Restylane or
- Group 2: left NLF: Restylane, right NLF: Radiesse.

Randomization will be stratified by investigative site and performed in blocks. All randomization codes will be generated by an electronic system. The system will allocate the subject's randomization number and will determine the subject's group assignment (Group 1 or Group 2) to be used at each injection visit. The randomization number for each subject will then be recorded in the eCRF.

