3.2 Effectiveness

The sample size considerations for the primary effectiveness endpoint (i.e., change from baseline to Week 24 after last injection on the WSRS [REDACTED]) are based on the following:

- Type I error, $\alpha = 0.05$ (two-sided) and
- Non-inferiority margin of 0.5.

When using the 118 subjects randomized for safety and applying a drop-out rate of 15% from randomization to the Per Protocol Set (PPS), [REDACTED]

[REDACTED] 100 subjects would be available for analysis of the primary effectiveness endpoint on PPS.

For analysis on the Full Analysis Set (FAS) even more subjects are expected. [REDACTED]

To ensure a reasonable number of subjects is enrolled per investigative site, the number of subjects treated at each site should not exceed 20 in case of seven recruiting sites, 24 in case of six recruiting sites, and 28 in case of five recruiting sites.

4 Analysis Sets

The following analysis sets will be defined:

- The randomized set is defined as all subjects randomized into the trial.
- The Safety Evaluation Set (SES) is defined as all subjects who are randomized and receive investigational product at least once.
- The Full Analysis Set (FAS) is defined as all subjects who are randomized, receive investigational product, and have at least one after-baseline effectiveness assessment.
- The Per Protocol Set (PPS) is the subset of subjects in the FAS who have no major protocol deviations or other events that impact analysis of the primary effectiveness endpoint. Final determination of which events lead to exclusion from PPS will be made prior to database close.

Analyses on the randomized subjects set, the FAS and the PPS will be performed *by randomized treatment*. For subjects randomized to “Group 1: left NLF: Radiesse, right NLF: Restylane”, the left NLF will be analyzed for Radiesse and the right NLF will be analyzed for Restylane, and for subjects randomized to “Group 2: left NLF: Restylane, right NLF: Radiesse”, the left NLF will be analyzed for Restylane and the right NLF will be analyzed for Radiesse.

5 Endpoints for Analysis

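### The primary model has no left/right side term, and the random-group main effect cannot stand in for one; the effect is small and adding side is nearly free

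*SAP*

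**What the plan says.** SAP 6.1.1.1 specifies a repeated-measures ANCOVA of WSRS change to Week 24, with treatment, site, "touch-up performed (i.e., yes/no), and random group" as fixed class effects, baseline WSRS as covariate, and treatment as the repeated factor with an unstructured covariance. Protocol 13.4.1.1 gives the same list under the older label: "touch-up performed (i.e., yes/no), and randomized sequence". A footnote in the SAP says that the relabelling changes nothing in the analysis. Neither list contains side of face or a treatment × random group term.

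Side is what is randomized. Under Protocol 13.2, "All eligible subjects will be randomized 1:1 to one of the following groups": Group 1 has Radiesse on the left and Restylane on the right, Group 2 the reverse, stratified by site and in blocks. Under Protocol 13.4.1.1, "The confirmatory analysis will be based on the PPS", and both documents allow for a 15% loss between randomization and that set.

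**The concern.** In a split-face trial, random group records which product went on which side. The model includes it only as a main effect, which describes whether subjects in one group change more than subjects in the other, averaged over both folds. That says nothing about a left/right difference, which shows up as a treatment × random group interaction. Any side difference therefore remains in the residual of the treatment contrast.

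Two things follow. The confidence interval for δ is somewhat wider than it need be. And if exclusions leave the two groups unequal in the PPS, the estimate of δ moves by a fraction of the side difference, up or down according to which group lost more subjects. Baseline WSRS cannot take over this role, because subjects must enter with the same score on both folds (Protocol 9.2.1).

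**Working it through.** **Inputs from the documents.** 118 randomized, 15% loss to the PPS, margin 0.5, upper limit of a two-sided 95% CI. The plan's own figure reproduces: 118 × 0.85 = 100.3, so 100 subjects in the PPS and 118 − 100 = 18 lost.

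**Assumed inputs.** Neither document shows the SD of the paired difference or any left/right effect. I take SD (within group) 0.5 to 0.7 and s 0.1 to 0.2 WSRS points, with complete pairs.

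**Algebra.** Let D be the Radiesse change minus the Restylane change in one subject. Then E(D) = δ + s in Group 1 and δ − s in Group 2. A group main effect adds the same constant to both folds and cancels from D. This is exact when all covariates are per subject. A REML fit to one simulated data set (n = 100, s = 0.3) gave δ = 0.1952 and SE 0.0725 for the planned model, equal to the plain mean of D and its SD/√n, and identical with random group dropped. Adding side brought the SE to 0.0664.

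**Standard error, n = 100, balanced groups.** Without side, √(SD² + s²)/√100; with side, SD/√100.

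| SD | s | SE without side | SE with side | Ratio |
|---|---|---|---|---|
| 0.5 | 0.1 | 0.0510 | 0.0500 | 1.02 |
| 0.7 | 0.1 | 0.0707 | 0.0700 | 1.01 |
| 0.5 | 0.2 | 0.0539 | 0.0500 | 1.08 |
| 0.7 | 0.2 | 0.0728 | 0.0700 | 1.04 |

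At SD 0.7 and s = 0.2 the CI half-width is 0.1445 without side and 0.1389 with it. Outside this range the loss grows: at SD 0.5 and s = 0.3 it is 0.1159 against 0.0992, or 17% wider.

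**Shift in δ.** Shift = s × (n1 − n2)/n. For 54/46 this is 0.1 × 8/100 = 0.008 or 0.2 × 8/100 = 0.016, about 2 to 3% of the margin.

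**Chance of such a split.** Start from 59/59 and remove 18 subjects at random, k of them from Group 1. Then n1 − n2 = 18 − 2k, which is 8 or more in absolute value when k ≤ 5 or k ≥ 13. The hypergeometric probability is 0.071, so about 0.035 in each direction.

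**One-sided error at δ = 0.5, nominal 0.025** (simulated, t-based interval, over the SD and s range above).

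| Situation | Without side | With side |
|---|---|---|
| Balanced groups | 0.018 to 0.024 | 0.025 |
| 54/46, shift against Radiesse | 0.008 to 0.018 | 0.025 |
| 54/46, shift in favour of Radiesse | 0.031 to 0.037 | 0.025 |

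Averaged over the random-exclusion model, the rates without side are 0.023 (s = 0.1, SD 0.5), 0.024 (0.1, 0.7), 0.018 (0.2, 0.5) and 0.021 (0.2, 0.7).

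**Power.** At δ = 0 it is above 0.999 with or without side. At δ = 0.25, s = 0.2, SD 0.7 and balanced groups it is 0.932 without and 0.942 with.

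**Touch-up coding.** Touch-up may be given in one fold or both (Protocol 10.5.2), and the visible text does not say whether the model term is per subject or per fold. In REML fits to 60 simulated data sets (54/46, s = 0.2, SD 0.7, 25% touch-up assumed), adding random group moved δ by less than 1e-14 with per-subject coding and by at most 0.0012 with per-fold coding. Mean SE without and with side was 0.0725 and 0.0699 (per subject), and 0.0733 and 0.0710 (per fold). The coding does not alter the finding.

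**The case against.** The strongest reply is that nothing here is an error. Sides are allocated 1:1 in blocks within site, which is the design's own protection against a side effect, and the unadjusted paired estimate is valid. The rates of 0.031 to 0.037 condition on an unlucky split with a probability of about 3.5%; averaged over chance exclusions the test stays below 0.025. Under random exclusion the shift in δ has mean zero, and the documents suggest no mechanism that would remove more subjects from one group. Nor do they suggest that the two folds respond differently: entry requires symmetrical folds, the same technique is sought on both sides, and each fold is treated to at least a 1-point improvement. Finally, text after the model is redacted, and the SAP's visible numbering goes from 6.1.1.1 to 6.1.1.3, so a supplementary analysis with side may exist.

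All of this stands as a limit on importance. It does not remove the point. Blocking balances the randomized subjects, while the confirmatory set is what remains after the planned 15% loss. The sentence that names the primary model's terms reads as complete, so a hidden supplementary analysis would not change that model. And the plan already includes the layout factor, in a form that does nothing for δ with complete pairs and per-subject covariates.

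**Conclusion.** The point holds as a small efficiency and robustness improvement. The planned model carries any left/right difference in the error of δ, and random group as a main effect does not remove it. For s up to 0.2 and SD 0.5 to 0.7, the cost is a standard error 1 to 8% too large and a shift of at most 0.016 at a 54/46 split. Type I error is not inflated overall, and the non-inferiority conclusion is unlikely to depend on it. These sizes rest on assumed values of s and SD. With s = 0.3 and SD 0.5 the loss in precision would no longer be trivial, though still in the conservative direction when the groups are balanced.

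**What to change.** In SAP 6.1.1.1, add side of face (left or right NLF) as a fixed class effect in the primary model. Equivalently, add treatment × random group and average the treatment LS means equally over the two groups. Random group may stay. The estimate of δ then no longer depends, through a side difference, on which group loses more subjects from the PPS. Record this as a change from Protocol 13.4.1.1 before unblinding.

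The cost is one model term, one degree of freedom and a sentence of SAP text. If there is no side effect, the SE at a 54/46 split and SD 0.7 goes from 0.7/√100 = 0.0700 to 0.5 × 0.7 × √(1/54 + 1/46) = 0.0702. No new data are needed, since Protocol 10.3 already requires the information: "Accurate documentation of which product (Radiesse or Restylane) is injected into which NLF".

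As a separate point of specification, the SAP should state whether touch-up is coded per subject or per fold.
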